2.2 Trial Diagram

Dose Escalation Phase

Dose Escalation Schedule During Radiotherapy Phase					
Dose Level	Dose				
	Pembrolizumab Vorinostat				
Level -1	200 mg IV every 3 weeks	100 mg/day orally on days 1-5 every week during radiotherapy			
Level 1	200 mg IV every 3 weeks	200 mg/day orally on days 1-5 every week during radiotherapy			
Level 2	200 mg IV every 3 weeks	300 mg/day orally on days 1-5 every week during radiotherapy			
	Dose Escalation S	Schedule During Maintenance Phase			
Dose Level Dose					
	Pembrolizumab	Vorinostat			
Level -1	200 mg IV every 3 weeks	200 mg/day orally 1 week on 1 week off after radiotherapy			
Level 1	200 mg IV every 3 weeks	300 mg/day orally 1 week on 1 week off after radiotherapy			
Level 2	200 mg IV every 3 weeks	400 mg/day orally 1 week on 1 week off after radiotherapy			

Twenty patients will be treated with vorinostat at MTD (from dose escalation phase), pembrolizumab, temozolomide and radiation

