Vorinostat will be administered orally at 200, 300 or 400 mg/day (based on dose level) on a 1 week on 1 week off schedule for 12 months. Vorinostat will start the day after completion of radiotherapy (+ 3 days). Safety of vorinostat 400 mg/day on a 1 week on 1 week off schedule in combination with maintenance temozolomide has been shown in a phase 1 study by Lee et al. 2012 [34].

Pembrolizumab 200 mg IV will continue every 3 weeks (+/-3 days) for 12 months or 18 infusions whatever comes first

Table 3 summarizes the doses for pembrolizumab and vorinostat during maintenance part of treatment.

Table 3 Dose Escalation Schedule for Pembrolizumab and Vorinostat maintenance part of treatment.

	Dose Escalation Schedule During Maintenance Phase					
Dose Level	Dose					
	Pembrolizumab	Vorinostat				
Level -1	200 mg IV every 3 weeks	200 mg/day orally 1 week on 1 week off after radiotherapy				
Level 1	200 mg IV every 3 weeks	300 mg/day orally 1 week on 1 week off after radiotherapy				
Level 2	200 mg IV every 3 weeks	400 mg/day orally 1 week on 1 week off after radiotherapy				

In all patients, treatment with study drugs will continue until confirmed disease progression, patient refusal, patient lost to follow up, unacceptable toxicity, completion of scheduled dosing, whichever occurs first, or the study is terminated by the Sponsor (Moffitt Cancer Center).

Dose Expansion Phase:

The vorinostat doses used in the dose expansion cohort will be MTD determined from the dose escalation phase.

Definition of Maximum Tolerated Dose:

The maximum tolerated dose (MTD) is the highest dose of vorinostat in combination with pembrolizumab, temozolomide during and after radiation therapy that does not cause unacceptable toxicity in more than one of six patients at that dose level. The MTD is defined as one dose level below the highest toxic dose (i.e., the DLT dose).

Details on preparation and administration of pembrolizumab (MK-3475) are provided in the Pharmacy Manual.

5.3.1 5.3.1 Definition of Dose-Limiting Toxicity

Toxicities will be graded in severity according to the guidelines outlined in the NCI-CTCAE version 4.0. Dose limiting CNS and non-CNS toxicities will be defined differently and will be based on events that occur during the study period. In order to be declared as dose-limiting toxicity, an adverse event must be related to pembrolizumab and/or vorinostat.

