- Grade 3 or 4 thrombocytopenia that is not associated with clinically significant bleeding that requires medical intervention, and improves by at least 1 grade within 14 days
- Isolated Grade 3 electrolyte abnormalities that are not associated with clinical signs or symptoms and are reversed with appropriate maximal medical intervention within 3 days
- Immune-related AEs are defined as AEs of an immune nature (ie, inflammatory) in the absence of a clear alternative etiology. In the absence of a clinically significant abnormality, repeat laboratory testing will be conducted to confirm significant laboratory findings prior to designation as a DLT. Laboratory abnormalities that are not deemed to be clinical significant will not be considered a DLT.

While the rules for adjudicating DLTs in the context of dose exploration are specified above, an AE not listed above may be defined as a DLT after a consultation with the sponsor and investigators, based on the emerging safety profile.

Dose escalation will be determined based on the occurrence of DLTs. For the purposes of determining whether to advance the dose levels, DLTs will be counted by patient. For all observed toxicities, subjects should be assessed for inter-current illness or other causes and treated as appropriate.

In the event of the development of any grade 3 or 4 toxicity felt to be at least possibly related to pembrolizumab, pembrolizumab will be held until resolution to grade 1 or baseline assuming that occurs within 6 weeks window. Treatment with pembrolizumab can be resumed after resolution of DLT to grade 1 or baseline except for following adverse events: Grade 4 infusion reactions, \geq Grade 3 pneumonitis, \geq Grade 3 nephritis, \geq Grade 3 colitis, increased alanine aminotransferase (ALT) or aspartate aminotransferase (AST) greater than 5 times upper limit of normal or total bilirubin greater than 3 times upper limit of normal.

Dose escalation for vorinostat will follow the standard 3+3 design. The enrollment to expansion cohort for radiotherapy phase will be delayed for 6 weeks after the completion of radiation therapy by the last patient enrolled at the MTD dose level for radiation therapy phase. The enrollment to expansion cohort for maintenance phase will be delayed for 4 weeks after the start day of maintenance dose of vorinostat [Cycle 1 Day 43 (+/-3)] by the

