last patient enrolled at the MTD dose level for maintenance phase. This period will allow monitoring potential delayed toxicities. Dose escalation/de-escalation will proceed according to the following scheme.

Table 3 Dose Escalation Decision Rule

Number of Patients with DLT at a Given Dose Level	Escalation Decision Rule	
0 out of 3	Enter 3 patients at the next dose level.	
≥ 2	Dose escalation will be stopped. This dose level will be declared the maximally administered dose (highest dose administered). Three (3) additional patients will be entered at the next lowest dose level if only 3 patients were treated previously at that dose.	
1 out of 3 or ≥ 2 grade 2 CNS toxicities	 Enter at least 3 more patients at this dose level. If 0 of these 3 patients experience DLT, proceed to the expansion cohort. If 1 or more of this group suffer DLT, then dose escalation is stopped, and this dose is declared the maximally administered dose. Three (3) additional patients will be entered at the next lowest dose level if only 3 patients were treated previously at that dose. 	
≤1 out of 6 at highest dose level below the maximally administered dose	This is the dose to be used in the expanded cohort and will be considered recommended phase 2 dose.	

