5.10 Clinical Criteria for Early Trial Termination

Early trial termination will be the result of the criteria specified below:

- 1. Quality or quantity of data recording is inaccurate or incomplete
- 2. Poor adherence to protocol and regulatory requirements
- 3. Incidence or severity of adverse drug reaction in this or other studies indicates a potential health hazard to subjects
- 4. Plans to modify or discontinue the development of the study drug

In the event of Merck decision to no longer supply study drug, ample notification will be provided so that appropriate adjustments to subject treatment can be made.

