8.0 STATISTICAL ANALYSIS PLAN

8.1 Statistical Analysis Plan Summary

The number of patients for the dose escalation cohort will depend on the safety of dose level 1. There are two dose escalation levels and therefore the maximum sample size for the dose escalation cohorts will be 12 patients. In the dose expansion cohort, a total of 20 evaluable patients will be enrolled to confirm the safety at this dose and assess response to treatment. Therefore, the maximum sample size of the study is 32 patients. The sample size of 26 patients in treated at the MTD dose (20+3 patients from dose expansion cohort and 6+/-3 patients from the dose escalation) will give a two-sided 95% confidence interval (95%CI) of 39% to 79% for a 12-month overall survival rate of 60% when there is no censored data. If the 12-months overall survival rate increases to 80%, the corresponding 95%CI will be 60% to 93%. A two-sided 95% confidence interval for the median overall survival time is from 10 months to 23 months when the estimate of median overall survival time is 14.6 months and the percent censoring is anticipated to be 10%. These results assume Type-II Censoring and an exponential distribution of overall survival times with mean survival time of 21 months.

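### The 20-patient expansion is meant to confirm safety at the MTD, but no pre-specified DLT criterion says when safety is not confirmed or when accrual pauses

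*Combined protocol and SAP*

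**What the plan says.** Safety, tolerability and the MTD are the primary objective (section 3.1). Section 8.1 gives the expansion the task of confirming safety, alongside assessing response: "a total of 20 evaluable patients will be enrolled to confirm the safety at this dose". Section 2.2 fixes the dose for all of them: "Twenty patients will be treated with vorinostat at MTD (from dose escalation phase), pembrolizumab, temozolomide and radiation".

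The only toxicity limit is in section 5.3, where the MTD is the highest vorinostat dose in the combination "that does not cause unacceptable toxicity in more than one of six patients at that dose level". The escalation table in section 5.3.1 applies it. For the row "≤1 out of 6 at highest dose level below the maximally administered dose" the consequence reads "This is the dose to be used in the expanded cohort and will be considered recommended phase 2 dose". The dose therefore has its recommended phase 2 status before any expansion patient is treated.

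The stated use of DLT counts is escalation: "Dose escalation will be determined based on the occurrence of DLTs". The replacement rule in section 5.9, which introduces the DLT-evaluability criteria, is written for the escalation phase. Section 8.2 plans descriptive summaries, and every precision figure in section 8.1 concerns survival.

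Two safeguards carry no number. Section 5.10 lists among its reasons for early termination: "Incidence or severity of adverse drug reaction in this or other studies indicates a potential health hazard to subjects". Section 10.3 describes a monitoring committee that meets monthly, looks at adverse event frequencies, and may suspend or close the protocol.

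**The concern.** A cohort enrolled to confirm something needs a result that would fail to confirm it. Here there is none. The expansion has no DLT threshold, no interim look and no interval for the DLT rate, and no written rule lets its data revise a dose already labelled as recommended.

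This matters because the evidence entering the expansion is thin. A 3+3 on six patients cannot separate an acceptable DLT rate from one well above the protocol's 1-in-6 tolerance. If the dose was wrongly cleared, the expansion is where that should show, and also where most patients are exposed. What is at stake is the exposure of up to 20 patients and the trial's ability to answer its primary question.

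**Working it through.** **Inputs.** Expansion of 20, escalation of 12, total 32, and 26 at the MTD (section 8.1); tolerance of 1 in 6 (sections 5.3 and 5.3.1); DLT windows (section 5.3.1); 24-month enrolment (section 1.0). The true DLT rates below are assumptions, since the documents give none.

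**The plan's own figures.** 12 + 20 = 32. Exact (Clopper-Pearson) limits with n = 26 and x = 26p give 39.1% to 78.5% at 60% and 59.8% to 93.0% at 80%. For the median, 2r × 14.6/χ² on 2r degrees of freedom with r = 23 events gives 10.1 to 23.0 months. All agree with section 8.1 after rounding, and none concerns toxicity.

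**Evidence behind the MTD.** An observed 1/6 has an exact 95% interval of 0.4% to 64%; 0/6 has 0% to 46%.

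**Chance that a single dose level is cleared at true rate p.**

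- At most 1 in 6 required: (1−p)^6 + 6p(1−p)^5. At p = 1/3: 0.088 + 0.263 = 0.351. At p = 0.40: 0.047 + 0.187 = 0.233.
- 0 in 3 also sufficient: (1−p)^3 + 3p(1−p)^2 × (1−p)^3. At p = 1/3: 0.296 + 0.132 = 0.428. At p = 0.40: 0.216 + 0.093 = 0.309.

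**What the expansion could show without consequence.** At p = 0.40 the expected count is 20 × 0.40 = 8 DLTs. An observed 8/20 has an exact 95% interval of 19% to 64%, wholly above 1/6 (16.7%). It would trigger no pre-specified numeric rule.

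**What a boundary would do.** Illustration: pause at ≥3/5, ≥4/10 or ≥6/15, with ≥7/20 as the final criterion only, because all 20 are enrolled by then. At each look the binomial distribution of the DLT count is carried forward from the paths that have not yet crossed. The mean enrolment shown assumes complete DLT data at each look and that a pause ends accrual.

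| True DLT rate | A pause look triggers | Including final ≥7/20 | Mean enrolment |
|---|---|---|---|
| 1/6 | 9% | 10% | 19.0 |
| 1/3 | 52% | 62% | 14.0 |
| 40% | 71% | 81% | 11.7 |
| 50% | 90% | 96% | 8.8 |

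At intermediate rates of 20% and 25%, the boundary including the final criterion triggers with probability 18% and 33%.

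Detail at 40%: first crossings at 5, 10, 15 and 20 patients have probability 0.317, 0.318, 0.074 and 0.104. The first three sum to 0.709 and all four to 0.813. Mean enrolment is 5(0.317) + 10(0.318) + 15(0.074) + 20(1 − 0.709) = 11.7. Patients with a DLT avoided: 0.40 × (20 − 11.7) = 3.3.

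**Allowing for the DLT window.** In the radiotherapy phase, about 6 weeks of radiation plus 6 weeks of follow-up is about 12 weeks, or 2.8 months. At 32/24 = 1.33 patients a month, about 1.33 × 2.8 = 3.7, say 4, more patients enrol meanwhile. Mean enrolment at 40% becomes 9(0.317) + 14(0.318) + 19(0.074) + 20(0.291) = 14.5, and patients with a DLT avoided 0.40 × (20 − 14.5) = 2.2.

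**The case against.** The strongest reply is that oversight exists. The committee in section 10.3 sees adverse events monthly and can suspend or close the trial, section 5.10 allows termination on adverse reactions, section 5.3.1 imposes a wait before the expansion opens, and section 5.3.2.2 holds or stops drugs in individual patients. This stands in part. A reader might infer that all 20 patients would inevitably be treated at a wrongly cleared dose, or that nothing could overturn the MTD. The documents do not support that, because the committee has the power to act. They do show that it has no DLT rate to act on, that the wait comes before the expansion and not within it, and that the drug-modification rules act patient by patient.

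A second reply is that 43% and 31% overstate the chance of wrongful clearance. This also stands. The MTD definition and the table row that selects the expansion dose both refer to six patients, so 35% and 23% fit them better. The higher pair applies only if 0 in 3 is enough. The concern survives either reading.

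Third, a boundary saves less than it first appears to. The look at 20 cannot protect anyone, and the 12-week window erodes the earlier looks; the figures above show both effects.

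Fourth, the DLT definition in section 5.3.1 is not expressly confined to escalation, so it would go too far to say that DLTs are undefined in the expansion. What is missing is a rule that uses them.

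Finally, section 5.3 reports that the radiotherapy-phase vorinostat dose was reduced because of DLT and is now being expanded. That does not show that the present dose is too toxic: the same section calls it well tolerated.

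**Conclusion.** The concern holds in this form: no pre-specified DLT criterion governs the expansion, so up to 20 patients could be treated at a dose wrongly cleared by the 3+3, with only discretionary review to prevent it. At assumed true DLT rates of 1/3 and 40%, the chance of clearing a single dose level is 35% and 23% (43% and 31% on the looser reading). These are not probabilities that the whole escalation ends at such a dose.

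The size of the benefit depends on the assumed rates, the boundary chosen and how promptly DLT data are complete. At 40%, about 3 fewer patients would have a DLT with complete data at each look, and about 2 fewer with an overrun of four. The particular boundary is not the point. Three other sets built on different thresholds trigger with probability 5% to 16% at a true rate of about 1/6 and 58% to 90% at 40%. The gap deserves correction because it concerns the primary objective and is cheap to close.

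**What to change.** In section 8.1:

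- State that the DLT definition and windows in section 5.3.1 and the evaluability criteria in section 5.9 also apply in the expansion, with DLTs counted separately for the radiotherapy and maintenance phases.
- Add a numeric boundary built on the 1-in-6 tolerance that pauses accrual for review by the monitoring committee, and give its operating characteristics. The illustration is ≥3/5, ≥4/10 or ≥6/15 for a pause, with ≥7/20 only as the final criterion for safety not confirmed.
- Say how patients still inside the DLT window, and those already in the expansion, are counted at each look.
- Report the final DLT rate at the MTD with an exact 95% interval.

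The sponsor chooses the acceptable rate and the boundary. Crossing it prompts review and prescribes no change of dose or treatment.

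The cost is one SAP paragraph and no extra patients. The chance of an unnecessary trigger is about 10% at a true rate of 1/6, rising to 18% at 20% and 33% at 25% if those rates are judged acceptable. Accrual may be delayed: holding it for complete data at all three pause looks could add up to about 3 × 12 = 36 weeks, whereas letting it run gives up part of the saving as shown.

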3.2 Secondary Objective(s) & Hypothesis(es)

(1) **Objective**: To evaluate the 12 months and 24 months survival rate in patients with newly diagnosed glioblastoma who are treated with pembrolizumab in combination with vorinostat and standard treatment with radiotherapy and temozolomide.

Hypothesis: Addition of pembrolizumab and vorinostat to standard treatment with radiotherapy and temozolomide will augment the survival.

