8.2 Statistical Analysis Plan

Data will be summarized overall using descriptive statistics. Continuous data will be summarized with number of patients (n), mean, median, minimum, maximum, standard deviation, coefficient of variation, and geometric mean (where applicable). Categorical data will be summarized using frequency counts and percentages. Time-to-event outcome data will be summarized using Kaplan-Meier survival curve and median survival time.

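### The 10 to 23 month interval for median survival in section 8.1 belongs to an exponential estimate, whereas section 8.2 plans a Kaplan-Meier median and names no interval method

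*Combined protocol and SAP*

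**What the plan says.** Section 8.1 (Statistical Analysis Plan Summary) describes the precision expected at the MTD. It starts from "The sample size of 26 patients in treated at the MTD dose" and gives intervals for the 12-month survival rate. It then turns to the median: "A two-sided 95% confidence interval for the median overall survival time is from 10 months to 23 months". The inputs given for this interval are an estimated median of 14.6 months and 10% censoring. The model is stated directly afterwards: "These results assume Type-II Censoring and an exponential distribution of overall survival times with mean survival time of 21 months".

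Section 8.2 (Statistical Analysis Plan) sets out the analysis: "Time-to-event outcome data will be summarized using Kaplan-Meier survival curve and median survival time". It mentions no exponential or other parametric model, no confidence interval for the median and no interval method.

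Section 3.2 gives the survival objective: "To evaluate the 12 months and 24 months survival rate in patients with newly diagnosed glioblastoma". The median is not named there.

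**The concern.** An interval quoted in a sample size section tells readers how precise the eventual result should be. That works only if the interval belongs to the estimator that will be reported. Here the precision statement uses one estimator (exponential, all events contributing to a single rate) and the analysis uses another (Kaplan-Meier, no distributional form).

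The two differ in precision even when the exponential model is exactly true, because the Kaplan-Meier median uses only the shape of the curve near its midpoint. If 10 to 23 months is read as what the planned analysis will give, the trial will usually turn out less informative about median survival than section 8.1 suggests.

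**Working it through.** **Inputs.** From section 8.1: n = 26; estimated median 14.6 months; 10% censoring, so 0.90 × 26 = 23.4 events, taken as r = 23; exponential survival with mean 21 months (21 × ln 2 = 14.56, in line with 14.6); Type-II censoring; two-sided 95%. From section 8.2: Kaplan-Meier curve and median. *Assumption:* the Kaplan-Meier interval is a Brookmeyer-Crowley interval. Because the plan names no transformation, three are shown.

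**1. Reproduce the stated figure.** For exponential data stopped at the r-th event, 2r × (estimate / true value) follows a chi-square distribution with 2r degrees of freedom. The limits for the median are 14.6 × 2r / χ²(0.975; 2r) and 14.6 × 2r / χ²(0.025; 2r).

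- Lower: 14.6 × 46 / 66.62 = 10.08 months.
- Upper: 14.6 × 46 / 29.16 = 23.03 months.

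This is the stated 10 to 23. With 22 or 24 events the result is 10.0 to 23.3 or 10.2 to 22.8. Exponential Wald limits (8.6 to 20.6) and log-Wald limits (9.7 to 22.0) do not match, so the figure is the exact exponential interval.

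**2. Compare large-sample standard errors.**

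- Kaplan-Meier median: √(0.25/n) / f(median), with f(median) = 0.5/mean. This reduces to mean/√n = 21.06/√26 = 4.13 months, where 21.06 = 14.6/ln 2. Censoring after the 23rd of 26 events falls beyond the median and does not enter.
- Exponential estimate: 14.6/√23 = 3.04 months.
- Ratio: 4.13/3.04 = 1.36.

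**3. Check with order statistics, ignoring censoring.** The 8th and 19th of 26 exponential times have expected values of 7.6 and 26.6 months (coverage 97.1%). The 9th and 18th have 8.7 and 23.9 months (coverage 92.4%). A 95% distribution-free interval lies between these two.

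**4. Simulate under the plan's own assumptions** (10,000 trials, n = 26, exponential with median 14.6, stopped at 23 events). With Greenwood sum V(t), the interval contains the times at which the pointwise limits for S(t) include 0.5:

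- plain: S ± 1.96 S√V;
- log: S × exp(±1.96√V);
- log-log: ln(−ln S) ± 1.96√V / |ln S|.

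| Interval | Median limits (months) | Median width | Ratio to 12.7 | Wider than exponential in same trial | Coverage |
|---|---|---|---|---|---|
| Exponential | 9.9 to 22.6 | 12.7 | 1 | n/a | 94.7% |
| Kaplan-Meier, plain | 8.4 to 23.4 | 14.5 | 1.14 | 70% | 92.3% |
| Kaplan-Meier, log-log | 7.2 to 23.4 | 15.7 | 1.24 | 80% | 94.6% |
| Kaplan-Meier, log | 8.4 to 28.8 | 20.0 | 1.57 | 96% | 95.8% |

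Against the stated width of 23 − 10 = 13 months, the ratios are 14.5/13 = 1.12, 15.7/13 = 1.21 and 20.0/13 = 1.54.

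**5. Match the plan's condition that the estimate is 14.6.** Among simulated trials with a Kaplan-Meier median within 1 month of 14.6, typical limits are 7.8 to 23.7 (log-log), 9.1 to 23.7 (plain) and about 9 to 29 (log).

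**6. Where the change falls** (table in step 4, against 9.9 to 22.6). Plain moves the lower limit by 1.5 months and the upper by 0.8. Log-log moves them by 2.7 and 0.8. Log moves them by 1.5 and 6.2. So the shift is mainly at the lower limit for plain and log-log, and mainly at the upper limit for log.

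**The case against.** The case for leaving the text alone has several sound parts.

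- *The number is right and its model is stated.* This stands. A reader might infer an arithmetic error or a hidden assumption; the documents support neither. Disclosure does not remove the mismatch, though. The Kaplan-Meier interval is typically wider even when the disclosed exponential model holds, and section 8.1 does not say that its figure comes from an estimate that section 8.2 does not plan.
- *Planning under a parametric model and summarising non-parametrically is ordinary practice.* True, and the two sections do not strictly contradict each other. The planning figure still has to be labelled so that it is not taken as the precision of the reported result.
- *The plan specifies no Kaplan-Meier interval, so any comparison rests on an assumed method.* This stands. The widening runs from 14% to 57% in median width depending on the transformation, so no single figure can be attributed to the plan. This is also a reason to name a method.
- *The Kaplan-Meier interval is not always wider.* Correct. It was no wider in about 30% of simulated trials for plain limits, 20% for log-log and 4% for log.
- *Little depends on it.* This stands. The primary objective is safety and the MTD. The survival objective is the 12- and 24-month rates. The maximum of 32 patients is 12 in escalation plus 20 in expansion.

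A reader might also point to the 24-month enrolment and 36-month duration and expect a much wider or open-ended interval. That concerns whether 10% censoring is realistic, which is a separate question; it is not evidence for this mismatch.

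**Conclusion.** The point holds as a mismatch between sections 8.1 and 8.2, and it is minor. The 10 to 23 month interval is a correct, openly labelled exponential interval with 23 events. The planned Kaplan-Meier median would typically carry an interval of about 8 to 24 months (log-log), 9 to 24 (plain) or 9 to 29 (log) when the estimate is near 14.6. This rests on the plan's own n = 26, 23 events and exponential survival, and on an assumed Brookmeyer-Crowley interval.

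It would be too strong to conclude that the sample size is wrong or that the survival objective is compromised. No decision rule, test or sample size in the documents uses this interval.

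**What to change.** Preferred: in section 8.1, give the expected interval for the Kaplan-Meier median, about 8 to 24 months with 23 events, and in section 8.2 name the Brookmeyer-Crowley method with log-log limits. This needs no distributional assumption at analysis, and log-log coverage in the simulation was close to nominal (94.6%, against 92.3% for plain).

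Alternative: keep 10 to 23 months and pre-specify in section 8.2 the exponential estimate and exact chi-square interval to which it belongs, alongside the Kaplan-Meier curve.

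The cost is about one sentence in section 8.1 and one in 8.2. No patient, visit or sample size changes. Under the preferred option the stated precision becomes slightly less favourable.

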1.0 TRIAL SUMMARY

Abbreviated Title	Phase I trial of pembrolizumab with vorinostat and temozolomide for newly diagnosed glioblastoma
Trial Phase	Ib
Clinical Indication	Newly diagnosed glioblastoma
Trial Type	Open label
Type of control	Not applicable
Route of administration	Intravenous, Oral
Trial Blinding	Not applicable
Treatment Groups	1 Group
Number of trial subjects	32
Estimated enrollment period	24 months
Estimated duration of trial	36 months
Duration of Participation	24 months
Estimated average length of treatment per patient	15 months

[figure not shown]

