5.8 Subject Withdrawal/Discontinuation Criteria

Subjects may withdraw consent at any time for any reason or be dropped from the trial at the discretion of the investigator should any untoward effect occur. In addition, a subject may be withdrawn by the investigator or the Sponsor (Moffitt Cancer Center) if enrollment into the trial is inappropriate, the trial plan is violated, or for administrative and/or other safety reasons. Specific details regarding discontinuation or withdrawal are provided in Section 7.1.4 – Other Procedures.

A subject must be discontinued from the trial for any of the following reasons:

• The subject or legal representative (such as a parent or legal guardian) withdraws consent.

- Unacceptable adverse experiences as described in Section 5.3.2
- Confirmed radiographic disease progression

Note: For unconfirmed radiographic disease progression, please see Section 7.1.2.6

Note: A subject may be granted an exception to continue on treatment with confirmed radiographic progression if clinically stable or clinically improved, please see Section 7.1.2.6

- Unacceptable adverse experiences as described in Section 5.3.2
- Intercurrent illness that prevents further administration of treatment
- Investigator's decision to withdraw the subject
- The subject has a confirmed positive serum pregnancy test
- Noncompliance with trial treatment or procedure requirements
- The subject is lost to follow-up
- Completed 15 months of uninterrupted treatment with pembrolizumab or 20 administrations of study medication, whichever is later.

Note: 15 months of study medication is calculated from the date of first dose.

Administrative reasons

The End of Treatment and Follow-up visit procedures are listed in Section 6 (Protocol Flow Chart) and Section 7.1.5 (Visit Requirements). After the end of treatment, each subject will be followed for 30 days for adverse event monitoring (serious adverse events will be collected for 90 days after the end of treatment as described in Section 7.2.3.1). Subjects who discontinue for reasons other than progressive disease will have post-treatment follow-up for disease status until disease progression, initiating a non-study cancer treatment, withdrawing consent or becoming lost to follow-up. After documented disease progression each subject will be followed by telephone for overall survival until death, withdrawal of consent, or the end of the study, whichever occurs first.

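### The stated 24-, 24- and 36-month durations do not fit together, survival follow-up has no dated end, and the 10% censoring behind the median-survival interval is not expected within 36 months

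*Combined protocol and SAP*

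**What the plan says.** The trial summary (Section 1.0) lists "Estimated enrollment period 24 months", "Duration of Participation 24 months" and "Estimated duration of trial 36 months". It also lists "Estimated average length of treatment per patient 15 months".

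Section 3.2 sets the secondary objective: "To evaluate the 12 months and 24 months survival rate in patients with newly diagnosed glioblastoma".

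Section 5.8 says that after documented progression "each subject will be followed by telephone for overall survival until death, withdrawal of consent, or the end of the study, whichever occurs first". Section 7.1.5.4.1 repeats this rule, with calls every 12 (± 4) weeks. Neither section gives a date, a follow-up length or a number of deaths that defines the study end.

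Section 8.1 bases its precision statement on 26 patients treated at the MTD. For an estimated median of 14.6 months it gives 10 to 23 months, where "the percent censoring is anticipated to be 10"%. It adds: "These results assume Type-II Censoring and an exponential distribution of overall survival times with mean survival time of 21 months". Section 8.2 plans Kaplan-Meier curves and median survival, and sets no analysis date.

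**The concern.** Type-II censoring means follow-up until a fixed number of deaths. Ten per cent censoring of 26 patients means waiting for about 23 deaths. The only calendar figure for the end of the trial is the 36-month estimate, and with a median survival of 14.6 months and enrollment lasting up to 24 months, that many deaths by month 36 looks unlikely. Separately, the three durations leave late enrollees without the 24 months that the secondary objective needs.

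At stake are the precision quoted for median survival, the number of patients who inform the 24-month rate, and whether the timing of the survival analysis is fixed in advance in an open-label, single-group trial.

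**Working it through.** **Inputs from the documents.** Section 8.1: n = 26, median 14.6 months, exponential survival, Type-II censoring, 10% censored, two-sided 95%. Section 1.0: enrollment 24, participation 24 and trial 36 months. The mean is θ = 14.6 / ln 2 = 21.06 months, which agrees with the stated 21.

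**Assumptions not in the documents.** No loss to follow-up. The 26 MTD patients accrue uniformly from month s to month 24, with s = 0, 6 or 12. Later starts are shown because Section 5.3.1 delays expansion enrollment until the observation window of the last MTD-level patient has passed. Enrolling everyone on day 1 gives the lower bound on censoring.

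**1. The stated interval.** With r deaths the limits are 14.6 × 2r / χ²(0.975; 2r) and 14.6 × 2r / χ²(0.025; 2r).
- r = 23 (11.5% censored): 671.6 / 66.617 = 10.08 and 671.6 / 29.160 = 23.03.
- r = 24 (7.7% censored): 10.15 and 22.79.

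The stated 10 to 23 reproduces. The 12-month exact binomial intervals also reproduce: 39.1% to 78.5% at 60%, and 59.8% to 93.0% at 80%.

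**2. The durations.** 24 + 24 = 48, against 36. A patient enrolled at month e has at most 36 − e months of follow-up by month 36, which reaches 24 only if e ≤ 12. A patient enrolled at month 24 with the average 15 months of treatment is treated to month 39, already past month 36.

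**3. Expected censoring at a calendar close T.**
- All enrolled on day 1, T = 36: exp(−36/21.06) = 0.181. No accrual pattern gives less.
- Uniform accrual from s to 24: θ/(24 − s) × [exp(−(T − 24)/θ) − exp(−(T − s)/θ)]. For T = 36 and s = 0 this is 0.878 × (0.566 − 0.181) = 0.338.

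The expected deaths, 26 × (1 − censoring), are then put into the formula of step 1:

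| Close | MTD accrual (assumed) | Censored | Expected deaths | Approx. interval for the median (months) |
|---|---|---|---|---|
| 36 | 0–24 | 34% | 17.2 | 9.6 to 25.0 |
| 36 | 6–24 | 38% | 16.1 | 9.5 to 25.5 |
| 36 | 12–24 | 43% | 14.8 | 9.3 to 26.2 |
| 48 | 0–24 | 19% | 21.0 | 9.9 to 23.6 |
| 48 | 6–24 | 21.5% | 20.4 | 9.9 to 23.8 |
| 48 | 12–24 | 24% | 19.7 | 9.8 to 24.0 |

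The intervals are approximate because the number of deaths is random under a calendar close. For accrual over months 0–24, simulation of calendar-censored trials gave median limits of 9.5 to 24.8 (month 36) and 9.9 to 23.4 (month 48), with coverage close to 95%.

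**4. When 10% would be reached.** In 200,000 simulated trials with accrual over months 0–24, the 23rd death falls at a median of about month 55 (10th to 90th percentile 43 to 69). The chance of 23 deaths by month 36 is about 1%, and about 28% even if all enrol on day 1.

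**5. The 24-month rate.** S(24) = exp(−24/21.06) = 0.320, so with full follow-up 26 × 0.320 = 8.3 patients are at risk at month 24. With a month-36 close and accrual over months 0–24, half of the patients can reach 24 months, which leaves 4.2 at risk. The Greenwood standard error rises from 0.091 to 0.103. With accrual over 6–24, one third can reach 24 months (2.8 at risk). With accrual over 12–24, essentially none can.

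**6. Sensitivity to survival.** For mean survival of 18 to 30 months and accrual over months 0–24, censoring is 28% to 46% at month 36 and 15% to 31% at month 48.

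**The case against.** The strongest reply is that Section 8.1 is consistent with itself. It names Type-II censoring, and about 23 deaths of 26 give exactly the interval it states. That stands: a reader might infer that the interval is miscalculated, and it is not. What is missing is the operational trigger and its calendar timing.

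Second, the 36 months is labelled an estimate and the study end is undated, so one cannot say that the plan rules out longer follow-up. That also stands. The point is that the only timing given does not deliver the 10%, and nothing else fixes the cutoff.

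Third, a reader might infer that the 24-month participation entry caps survival follow-up, which would put expected censoring at 32% or more whatever the closing date. The documents do not support this. Sections 5.8 and 7.1.5.4.1 follow survival to death, withdrawal of consent or study end and name no such limit, and the summary entry can be read as treatment plus visits.

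Fourth, the planned analysis is descriptive Kaplan-Meier, which handles censoring, and the exponential interval is only a planning illustration. This limits the consequence but does not remove the mismatch.

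**Conclusion.** The point holds and is minor. The three durations cannot give 24 months to anyone enrolled after month 12, the end of survival contact is undefined, and 10% censoring is not expected by month 36. The 18% floor needs only the SAP's survival model and a month-36 close. The 34% to 43% range also needs the assumed accrual patterns.

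The effect on precision is modest: the lower limit moves down by about half a month to three quarters of a month, and the upper limit up by two to three months. The 24-month rate loses more, since few or none of the MTD patients would be at risk at month 24. It does not follow that a 24-month Kaplan-Meier rate is generally out of reach. It can be estimated where some patients reach 24 months, but it would rest on few of them.

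The MTD objective and the 12-month intervals are unaffected, and no decision rule uses the median interval.

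**What to change.** 1. Section 1.0: make the enrollment, participation and trial durations agree.
2. Sections 5.8 and 7.1.5.4.1: define the end of the study for survival contact.
3. Section 8.1: choose one of the following.
   - (a) Keep Type-II censoring. State the death count that triggers the analysis (23 of 26) and its expected timing (about month 55 from first enrollment with accrual over months 0–24, later if MTD accrual starts late), and align the trial duration with it.
   - (b) Keep a calendar close. Restate the censoring and the interval from the sponsor's own projected accrual of the MTD patients, and label the interval approximate. As a guide, expect about 34–43% and roughly 9.5 to 25–26 months at month 36, or about 19–24% and roughly 9.8–9.9 to 23.6–24.0 months at month 48. Report the 24-month Kaplan-Meier rate with its number at risk.

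**Cost.** A month-36 close costs only wording and a slightly wider stated interval. A later close adds telephone contact for the patients still alive at month 36: about 11 of 32 (32 × 0.338 = 10.8, if all 32 accrue uniformly over 24 months). Twelve more months is about 3 to 6 calls for each patient who survives them. The survival report comes later, by about 12 months with a month-48 close and by more under (a). No extra patients are needed.
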